9.3.2 Secondary Effectiveness Endpoints

The secondary effectiveness variables:

- Good clinical outcome at 30 days post-procedure. Patients meeting one of the following are evaluated as having good clinical outcome: 10 points or more improvement in the NIHSS at Discharge; a NIHSS score of 0-1 at Discharge; 30-day mRS score of 0-2.
- Good neurological outcome at 90 days post-procedure. Patients meeting one of the following are evaluated as have a good neurological outcome at 90 days:
 - mRS score ≤ 2 at 90 days
 - mRS score at 90 days equal to the pre-stroke mRS score (if the pre-stroke mRS score was higher than 2)
 - 10 or more points improvement on the NIHSS score at 90 days
- The proportion of patients with a modified Rankin Scale (mRS) of ≤ 2 at 90 days post procedure.

Frequency counts and percentage of patients within each category will be provided for categorical data. Estimates of the treatment differences and their 95% confidence intervals will be calculated. Patient rates will be compared between treatment groups with Fisher's exact test.

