Primary Effectiveness Non-Inferiority: The proportion of patients in the Penumbra System with Separator 3D group who experience TICI 2/3 is no more than .15 below the proportion of patients in the Penumbra System group who experience TICI 2/3.

Additional analyses conducted for secondary endpoints and subgroups will be presented, but not utilized in evaluating the study success or Penumbra System product claims.

3 Sample Size

Approximately 230 patients are to be randomized in a 1:1 ratio to the Penumbra System group (115 patients) or the Penumbra System with Separator 3D group (115 patients).

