9.2 Secondary Effectiveness Analysis

The secondary effectiveness variables:

- Good clinical outcome at 30 days post-procedure. Patients meeting one of the following are evaluated as having good clinical outcome: 10 points or more improvement in the NIHSS at Discharge; a NIHSS score of 0-1 at Discharge; 30-day mRS score of 0-2.

- Good neurological outcome at 90 days post-procedure. Patients meeting one of the following are evaluated as having a good neurological outcome at 90 days:
 - mRS score ≤ 2 at 90 days
 - mRS score at 90 days equal to the pre-stroke mRS score (if the pre-stroke mRS score was higher than 2)
 - 10 or more points improvement on the NIHSS score at 90 days
- The proportion of patients with a modified Rankin Scale (mRS) of ≤ 2 at 90 days post procedure.

Frequency counts and percentage of patients within each category will be provided for categorical data. Estimates of the treatment differences and their 95% confidence intervals will be calculated. Subject rates will be compared between treatment groups with Fisher's exact test.

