9.3 Handling of Multiplicity

There will be no adjustment for multiple comparisons between the Penumbra System versus the Penumbra System with Separator 3D on the primary effectiveness variable since the primary comparison is specified in the protocol. All other comparisons will be considered secondary analyses and will be adjusted using the Bonferroni correction.

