9.4 Effectiveness Subgroup Analysis

To evaluate the impact of baseline conditions on treatment effect, subgroup analyses will be performed for the primary effectiveness variable, TIC1 2-3, the secondary effectiveness variables (good clinical outcome at 30 days, 90-day mRS 0-2, good neurological outcome at 90 days) and the primary and secondary safety variables. The subgroups below will be used for these analyses:

- Age (< 65 , or ≥ 65)
- Baseline NIHSS (< 20 , or ≥ 20)
- Site of occlusion

The subgroup analysis will be conducted using a logistic regression with terms of treatment group and treatment-by-subgroup interaction. The primary statistical inference is the treatment-by-subgroup interaction, which is tested at the significance level of 0.100. These analyses will be performed on the Intent-To-Treat population. When the treatment-by-subgroup interaction is

statistically significant ($p \leq 0.100$) for a specific subgroup, the treatment group differences will be evaluated within each stratum of that subgroup.

10 Safety Analysis

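### The three clinical secondary endpoints are compared by unadjusted Fisher's exact test although baseline NIHSS and age are available; the power cost is real, but its size depends on assumptions the documents do not supply

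*SAP*

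**What the plan says.** SAP 9.2 covers three binary endpoints: good clinical outcome at 30 days, good neurological outcome at 90 days, and mRS of 2 or less at 90 days. It plans two outputs for each. One is estimation: "Estimates of the treatment differences and their 95% confidence intervals will be calculated". The other is a test: "Subject rates will be compared between treatment groups with Fisher's exact test". Protocol 9.3.2 has the same test: "Patient rates will be compared between treatment groups with Fisher's exact test". Neither section mentions covariates.

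Baseline NIHSS is in the Schedule of Assessments (Protocol Table 7) and, like age, is an entry criterion. SAP 9.4 brings both in as subgroup factors, with this aim: "To evaluate the impact of baseline conditions on treatment effect". They enter cut at 65 years and at NIHSS 20: "The subgroup analysis will be conducted using a logistic regression with terms of treatment group and treatment-by-subgroup interaction". That model tests interaction at 0.100. The regression in SAP section 11 serves only to examine centre differences and justify pooling. Randomisation is stratified by centre alone (SAP 5.2).

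On multiplicity, SAP 9.3 says of everything except the primary comparison: "All other comparisons will be considered secondary analyses and will be adjusted using the Bonferroni correction". It gives no count of comparisons. SAP section 2 limits the role of these endpoints: "Additional analyses conducted for secondary endpoints and subgroups will be presented, but not utilized in evaluating the study success".

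**The concern.** The primary endpoint is angiographic, so these three are the only effectiveness endpoints that describe how patients function. The plan commits to formal inference on them, with intervals, tests and a Bonferroni correction. It then chooses a test that runs below its nominal level and leaves unused two baseline variables that the SAP itself regards as worth examining for the same outcomes.

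There are two separate losses. Fisher's test is conservative at this sample size, and that costs power whatever the covariates do. Ignoring baseline NIHSS and age also leaves explainable variation in the comparison, if they are prognostic. Because stratification is by centre only, chance imbalance in either variable is described at baseline (SAP section 7) but not handled in the comparison. If no covariates are named in advance, any later adjustment will be post hoc.

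**Working it through.** **1. The plan's own figure.** The only power statement concerns the primary endpoint (SAP 3.2): 80% in both arms, margin 15 points, one-sided 0.05, 85% power.

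n = (1.645 + 1.036)² × (2 × 0.8 × 0.2) / 0.15² = 102.2, so 103 per arm. Power at 103 is 85.2%, and 103/0.9 gives 115. The stated figures reproduce. No such figure exists for any secondary endpoint.

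**2. Real level of Fisher's test.** Sum the two binomial probabilities, at a common rate p, over all tables with a two-sided Fisher p-value of 0.05 or less. For p from 25 to 50% the level is 3.3 to 3.9% at 103 per arm and 3.5 to 4.1% at 115. At p = 35% and 115 per arm it is 3.5%. At 0.05/3 (three comparisons, assumed because the count is not stated) it is 1.0 to 1.2% against 1.67%. This step needs only the sample size and a plausible rate.

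**3. Splitting the power loss by simulation.** All inputs here are assumed:
- 230 patients, 1:1, about 40% good outcome overall, treatment odds ratio 2.1 (roughly 32% against 48%)
- NIHSS mean 17.5, SD 5.5; age mean 67, SD 12; both held within the entry limits
- log odds ratio 0.08 to 0.16 per NIHSS point and 0.02 to 0.04 per year
- two-sided 0.05, no Bonferroni correction, 4,000 runs per row

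The adjusted test is the likelihood-ratio test for treatment in a logistic model with both covariates.

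| NIHSS, age log-OR | Fisher | Chi-square | Adjusted | Fisher's conservatism | Covariates |
|---|---|---|---|---|---|
| 0.08, 0.02 | 69.7% | 74.1% | 76.2% | 4.4 | 2.1 |
| 0.12, 0.03 | 63.5% | 68.2% | 73.4% | 4.7 | 5.2 |
| 0.16, 0.04 | 58.7% | 64.0% | 70.7% | 5.3 | 6.7 |

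The simulation error of each power figure is about √(0.7 × 0.3/4000) = 0.7 points. Runs of 1,500 on similar inputs put the covariate part between about 1 and 8 points and the Fisher part between about 4 and 6. With no treatment effect, the adjusted test rejected in 4.6 to 5.5% of runs, so the extra power is not bought with false positives.

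**4. A small true effect.** At odds ratio 1.25 (about 5 points) Fisher has 8.6 to 9.9% power and the adjusted test 12.5 to 13.2%, a total gain of 3 to 4 points.

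**5. Precision.** Across repeat runs the variance of the standardised risk difference is about 5 to 18% below that of the crude difference; some runs gave 3 to 4% at the weak end. At 40% and 115 per arm the crude 95% half-width is 1.96 × √(2 × 0.24/115) = 12.7 points. Multiplying by √0.95 and √0.82 gives 12.3 and 11.5.

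**6. Cross-check by formula.** Replace n with n/(1 − R²) in Φ[(d√n − 1.96√(2p̄q̄)) / √(p₀q₀ + p₁q₁)]. For 40% against 55% at 103 per arm, chi-square power is Φ[(1.522 − 1.384)/0.698] = 57.8%; exact Fisher power is 51.6%. At R² = 0.15, n becomes 103/0.85 = 121.2 and power 64.9%. Here 6.2 points come from dropping Fisher and 7.1 from the covariates. Over control rates of 25 or 40%, differences of 5 to 20 points, R² of 0.05 to 0.25, and alpha of 0.05 or 0.05/3, the total gain over Fisher runs from about 1 to just over 20 points.

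**The case against.** The strongest reply is that nothing turns on these tests. They are excluded from the success criterion and from product claims, they were never powered, and an unadjusted exact test is valid under randomisation without any model. This limits how serious the point is. It does not remove it, because the plan still commits to intervals, tests and a multiplicity correction for these endpoints.

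An odds ratio of 2.1 is also a large functional difference between two configurations of one aspiration system, in a trial that assumes equal angiographic success in both arms. That stands, and step 4 shows that little is gained at a small effect.

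SAP 9.4 treats NIHSS and age as possible effect modifiers, which does not show that they are strongly prognostic. That also stands; their strength is assumed here. For two of the three endpoints it may be weaker. Both composites can be met by a 10-point NIHSS improvement, which a patient entering at 8 or 9 cannot reach, so baseline NIHSS may act in opposite directions within the composite.

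Two stronger readings are tempting. A reader might infer that the missing covariates cost a fixed amount of power, say 6 to 10 points. The documents give no inputs from which to derive such a figure, and a good part of any total of that size comes from the choice of an exact test. A reader might also infer that Fisher's test widens the reported intervals. It need not: the 95% interval for the difference is a separate output in SAP 9.2, and only the lack of adjustment affects its width.

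**Conclusion.** The point holds as a low-cost improvement. It is not a flaw that threatens the trial. It is certain that the planned test is unadjusted, that no adjusted overall comparison is planned, and that Fisher's real two-sided level is about 3.3 to 4.1% at 103 to 115 per arm for true rates of 25 to 50%.

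The power cost is conditional. Under the step 3 assumptions it is about 4 to 6 points from Fisher's conservatism and about 2 to 7 from the covariates, with risk-difference variance about 5 to 18% lower under adjustment. For a true difference near 5 points the total is about 3 to 4 points. These figures are at two-sided 0.05; power under the planned Bonferroni correction is lower for both analyses, by an amount that depends on the unstated number of comparisons. The covariate gain is most plausible for 90-day mRS and may be smaller for the two composites.

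**What to change.** In SAP 9.2, with Protocol 9.3.2 aligned, pre-specify for each binary secondary effectiveness endpoint a logistic regression with treatment, baseline NIHSS and age, both continuous. Report the standardised risk difference, its 95% interval and its test as the main secondary analysis. This keeps the planned difference scale and avoids moving to a conditional odds ratio. Retain the Bonferroni correction, and show crude rates and Fisher's test as supportive. Site of occlusion is left out because neither document defines its categories.

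The cost is SAP wording and short code. No new data are needed, and SAP section 14 already allows a revised SAP. The downside is a model-based estimate tied to covariates named in advance. The primary analysis and the success criterion do not change.

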9.3 Handling of Multiplicity

There will be no adjustment for multiple comparisons between the Penumbra System versus the Penumbra System with Separator 3D on the primary effectiveness variable since the primary comparison is specified in the protocol. All other comparisons will be considered secondary analyses and will be adjusted using the Bonferroni correction.

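### SAP 9.3's Bonferroni rule is valid but dominated by Holm, and its literal scope is in tension with SAP 9.4: a minor, free improvement

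*SAP*

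**What the plan says.** SAP 9.3 exempts the primary effectiveness comparison from adjustment, "since the primary comparison is specified in the protocol". For everything else it says: "All other comparisons will be considered secondary analyses and will be adjusted using the Bonferroni correction". It does not give the number of comparisons or the familywise level.

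SAP 9.2 lists three secondary effectiveness endpoints:

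- "Good clinical outcome at 30 days post-procedure"
- "Good neurological outcome at 90 days post-procedure"
- "The proportion of patients with a modified Rankin Scale (mRS) of ≤ 2 at 90 days post procedure"

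Each is compared between arms by Fisher's exact test. The third is also one of the criteria that satisfy the second. On estimation, SAP 9.2 says: "Estimates of the treatment differences and their 95% confidence intervals will be calculated". It mentions no multiplicity adjustment of those intervals. SAP 5.1 runs every primary and secondary effectiveness endpoint in both the ITT and the per-protocol population.

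SAP 9.4 plans subgroup analyses by age, baseline NIHSS and site of occlusion for the effectiveness and safety variables. Of the interaction test it says: "The primary statistical inference is the treatment-by-subgroup interaction, which is tested at the significance level of 0.100". Where an interaction is significant, treatment differences are then evaluated within each stratum. No adjustment is stated for either step.

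SAP 2 rests study success on primary non-inferiority alone and keeps secondary endpoints and subgroups out of study success and product claims.

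**The concern.** There are two separate matters.

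**The procedure.** Holm controls the familywise error at the same level as Bonferroni, under the same conditions, and rejects every hypothesis that Bonferroni rejects. The usual reason to stay with Bonferroni is that it comes with simple simultaneous confidence intervals. This plan does not use that advantage, because the secondary intervals are ordinary 95% intervals.

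**The scope.** Read literally, the rule in SAP 9.3 covers every comparison except the primary one. The within-stratum treatment differences in SAP 9.4 are between-arm comparisons and are not primary, yet they carry no adjustment. The interaction tests have their own level, 0.100. Baseline testing (SAP 7) and the second analysis population are not addressed. A Bonferroni correction without a stated divisor cannot be applied reproducibly.

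At stake is how the trial's three measures of patient function are tested and reported. The primary conclusion is not at stake.

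**Working it through.** **1. The plan's own figure.** The documents give no power or adjusted alpha for any secondary endpoint. The only design figure to reproduce is the primary one (SAP 3.2).

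- n per arm = (1.645 + 1.036)² × 2 × 0.8 × 0.2 / 0.15² = 102.2, so 103.
- Power at 103: SE = √(2 × 0.8 × 0.2 / 103) = 0.0557, and Φ(0.15/0.0557 − 1.645) = 0.852, as in the SAS output.
- Attrition: 103/0.9 = 114.4, so 115.

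The figure reproduces.

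**2. Thresholds for three endpoints at familywise two-sided 0.05** (this level is an assumption, since SAP 9.3 states none).

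- Bonferroni: each p-value against 0.05/3 = 0.0167.
- Holm: smallest p against 0.05/3 = 0.0167, next against 0.05/2 = 0.025, largest against 0.05, stopping at the first failure.

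Holm's first threshold is Bonferroni's, and its later ones are larger. Holm therefore rejects whatever Bonferroni rejects, and the probability of at least one rejection is identical.

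**3. Size of the gain.** Assumptions, none of them in the documents: control rates 42%, 35% and 45%; the same true gain on all three endpoints; latent correlation 0.8; 103 per arm. Method: simulated correlated binary outcomes with Fisher's test. With 6,000 trials the Monte Carlo standard error is at most √(0.5 × 0.5/6,000) = 0.6 points.

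| True gain on all three | Average power, Bonferroni | Average power, Holm | Difference (points) |
|---|---|---|---|
| 5 points | 3.6% | 4.2% | 0.6 |
| 10 points | 13% | 15% | about 2.5 |
| 15 points | 35% | 41% | about 6 |
| 18 points | 52% | 59% | about 7.6 |

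At 18 points the chance of rejecting all three is 29% under Bonferroni and 45% under Holm. The chance of rejecting at least one is 74% under both. If only one endpoint has an 18-point effect, its power is 50.5% against 50.6%. With no true effect the familywise error is about 3% under both.

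A second set of assumptions (115 per arm, latent correlation 0.5, equal rates on all three endpoints) gives a similar picture, Bonferroni to Holm:

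- 40% v 50%: 15% to 18%
- 40% v 55%: 39% to 48%
- 40% v 60%: 69% to 79%
- 25% v 40%: 46% to 53%

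**4. What the undefined divisor could be.**

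- Three endpoints in one population: 3.
- Three endpoints in two populations: 3 × 2 = 6.
- Three endpoints plus interactions for four effectiveness variables in three subgroups: 3 + 4 × 3 = 15.

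For an assumed 35% v 55% at 103 per arm, exact Fisher power is 79% unadjusted, 64% at divisor 3, 56% at 6 and 45% at 15. The last value applies only if SAP 9.3 overrides the level that SAP 9.4 sets for itself.

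**The case against.** The strongest reply is that no planned decision depends on this. SAP 2 excludes secondary endpoints and subgroups from success and claims, no secondary endpoint was powered, and the sample size assumes equal TICI success in the two arms. The treatment differences and their 95% intervals are reported whichever procedure is used. Bonferroni is valid and prespecified. All of this stands, and it is why the point is minor.

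It can also be said that SAP 9.3 opens by speaking of comparisons between the two systems, that an interaction asks a different question, and that the specific level in SAP 9.4 should govern. That is a reasonable reading of the interaction tests. It does not settle the within-stratum treatment differences that follow a significant interaction, or the choice between ITT and per-protocol.

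Three stronger readings are tempting but not supported:

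- A reader might infer that the tension with SAP 9.4 itself costs power on the clinical endpoints. It does not. Following SAP 9.4's own level takes the interaction tests out of the family and makes the divisor smaller.
- A reader might infer that Holm makes it more likely that some clinical benefit is detected. It does not. It adds only second and third rejections, and two of the three endpoints overlap by definition.
- A reader might infer that correlation between the endpoints is what Holm exploits. It uses no correlation. At an 18-point gain, average power rises from 51.6% to 59.9% (8.3 points) at correlation 0.6, and by a slightly smaller 7.7 points at 0.8.

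**Conclusion.** The point holds as a minor, free improvement. The rule in SAP 9.3 is not an error, but Holm dominates it uniformly, and its family, divisor and level are unstated and in tension with SAP 9.4.

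Over the first set of assumptions, Holm adds roughly 0.6 to 7.6 points of average power per endpoint for true gains of 5 to 18 points. That range needs an effect on all three endpoints at once. The control rates, effects and correlation are assumptions, because the documents give none for these endpoints. No success criterion or product claim changes.

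**What to change.** Replace the second sentence of SAP 9.3 with wording to this effect: the family is the three secondary effectiveness endpoints of SAP 9.2 in one named analysis population, tested by the Holm step-down procedure at familywise two-sided 0.05; results in the other population, the SAP 9.4 interaction and within-stratum tests, and baseline comparisons are outside the family and reported with nominal p-values as exploratory. The population has to be named, because SAP 5.1 would otherwise turn three tests into six.

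The cost is a few lines of SAP text. The familywise guarantee, the sample size and the data collected do not change. The edit should be made before the SAP is signed off, which SAP 1 places before database lock. The separate Bonferroni rule for safety in SAP 10.4 is not covered by this wording and needs its own statement of family and level.

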9.4 Effectiveness Subgroup Analysis

To evaluate the impact of baseline conditions on treatment effect, subgroup analyses will be performed for the primary effectiveness variable, TIC1 2-3, the secondary effectiveness variables (good clinical outcome at 30 days, 90-day mRS 0-2, good neurological outcome at 90 days) and the primary and secondary safety variables. The subgroups below will be used for these analyses:

- Age (< 65 , or ≥ 65)
- Baseline NIHSS (< 20 , or ≥ 20)
- Site of occlusion

The subgroup analysis will be conducted using a logistic regression with terms of treatment group and treatment-by-subgroup interaction. The primary statistical inference is the treatment-by-subgroup interaction, which is tested at the significance level of 0.100. These analyses will be performed on the Intent-To-Treat population. When the treatment-by-subgroup interaction is

statistically significant ($p \leq 0.100$) for a specific subgroup, the treatment group differences will be evaluated within each stratum of that subgroup.

10 Safety Analysis

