The Penumbra System[®] is a new generation of neuro-embolectomy devices specifically designed to remove thrombus through aspiration.¹⁴⁻¹⁵ The System has received 510(k) clearance from the US FDA for an acute ischemic stroke recanalization indication. The pivotal trial for this clearance was a prospective, single arm, 125 patient study designed to assess the safety and effectiveness of the System to reduce clot burden in acute ischemic stroke, using the Concentric clot retriever (Mountain View, CA) as the predicate device (historical control).¹⁴ The results indicated that the Penumbra System was able to recanalize the site of primary occlusion in over 80% of the patients, which was higher than those reported for the Concentric clot retriever (43% to 54%), or the spontaneous reperfusion rate reported in the untreated control group in the PROACT-II study (18%).^{12,13,19} The high recanalization rate was independent of target vessel locations. Recanalization was successful in 82.6% of patients presenting with occluded target vessels in the ICA, and in 83% of patients presenting with occluded target vessels in the MCA. Among the patients recanalized with the device, 12.8% had procedural complications of which 3.2% were considered serious. None was associated with malfunction or breakage of the device. This procedural event rate is quite favorable when compared to the published rates for other intra-arterial interventions for acute stroke.^{12,13,19,20} These observations are indicative of the ability of the Penumbra System to access the cerebral arteries to safely recanalize the site of primary occlusions in most locations of the brain, and often, in patients with significant tortuosity that would normally hamper intracranial vascular access.

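### SAP 9.4 tests subgroup interaction on the primary safety endpoint, and on safety by site of occlusion, with no method for sparse cells; if the SAE rate is near 3.2%, the 10% gate runs at about 1% or 17% depending on an unstated choice of test.

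*SAP*

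**What the plan says.** Protocol 9.3.3 limits subgroup analysis to the effectiveness variables. SAP 9.4 repeats those and adds safety: the list ends with "90-day mRS 0-2, good neurological outcome at 90 days) and the primary and secondary safety variables". Under SAP 10.1 and 10.2 that means the 24-hour device- or procedure-related SAE (primary), all-cause mortality and symptomatic ICH.

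On method, SAP 9.4 states: "The subgroup analysis will be conducted using a logistic regression with terms of treatment group and treatment-by-subgroup interaction". On the decision rule: "The primary statistical inference is the treatment-by-subgroup interaction, which is tested at the significance level of 0.100". An interaction p-value at or below 0.100 leads to treatment comparisons within strata. On population: "These analyses will be performed on the Intent-To-Treat population".

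The factors are age at 65, "Baseline NIHSS (< 20 , or ≥ 20") and "Site of occlusion", the last without listed levels. Nothing says whether the interaction p-value is Wald, likelihood ratio or score, or what happens when a cell has no events. Fisher's exact test is planned for the overall safety comparisons (SAP 10.1, 10.2), but SAP 9.4 has no small-sample counterpart.

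**The concern.** Ordinary logistic regression breaks down when an arm-by-stratum cell has no events. The interaction estimate becomes infinite. The Wald standard error grows faster than the estimate, so its p-value goes to 1. The likelihood-ratio statistic stays finite, but its chi-square reference is poor with so few events.

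The interaction p-value is the stated trigger for looking inside strata. With a rare safety endpoint, a Wald gate hardly opens, even when all the events in one stratum fall in one arm. In a two-level subgroup a likelihood-ratio gate opens too often. Two analysts could follow SAP 9.4 faithfully and report opposite results from the same table.

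**Working it through.** **Inputs.** 115 per arm, 1:1 (SAP 3 and 3.2). Interaction level 0.100 (SAP 9.4). No document gives an expected rate for the primary safety endpoint. The nearest figure, in Protocol 1, is "12.8% had procedural complications of which 3.2% were considered serious", from a 125-patient single-arm study. I read both as percentages of patients (0.128 × 125 = 16 and 0.032 × 125 = 4). Symptomatic ICH was 11.2% in the same study. No mortality rate is given for it. Subgroup splits and site levels are not given, so those below are assumptions.

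**The plan's own figure.** SAP 3.2 reproduces: 80% v 80%, margin 15%, one-sided 0.05 and 85% power give 103 per group (power 0.852), and 103/0.9 rounds up to 115. The plan states no operating characteristics for the subgroup tests.

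**Expected events per arm.** Primary safety: 0.032 × 115 = 3.7. Symptomatic ICH: 0.112 × 115 = 12.9.

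**Probability of an empty cell.** P = 1 − ∏[1 − (1 − p)^n] over the arm-by-stratum cells.
- p = 0.032, strata 58/57 per arm: (0.968)^58 = 0.152 and (0.968)^57 = 0.157, so P = 1 − (0.848 × 0.843)² = 0.49.
- p = 0.032, strata 35/80 (about 30/70): 0.320 and 0.074, so P = 1 − (0.680 × 0.926)² = 0.60.
- p = 0.032, by site: 0.94 with three levels (25/70/20 per arm), over 0.99 with four (25/60/20/10).

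**Actual size of the nominal 10% test.** 60,000 simulated tables per setting with no interaction; full model (treatment, subgroup, interaction); Wald counted as non-significant when a cell is empty.

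| Rate | Strata per arm | P(empty) | Wald | Likelihood ratio |
|---|---|---|---|---|
| 3.2% | 58/57 | 0.49 | 0.8% | 16.5% |
| 3.2% | 40/75 | 0.56 | 0.6% | 15.6% |
| 3.2% | 30/85 | 0.66 | 0.3% | 13.6% |
| 6% | 58/57 | 0.11 | 5.3% | 13.6% |
| 9% | 58/57 | 0.02 | 8.6% | 11.5% |
| 11.2% (ICH) | 58/57 | 0.004 | 9.6% | 11.0% |
| 11.2% (ICH) | 30/85 | 0.06 | 6.5% | 12.4% |

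By site at 3.2%, Wald never rejected; likelihood-ratio size was 11.6% (three levels) and 7.8% (four). The 17% figure therefore belongs to two-level subgroups. For symptomatic ICH by site, P(empty) is 0.26 with three levels and about 0.64 with four, with likelihood-ratio size about 15%.

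**Firth penalised likelihood-ratio test.** Size at 3.2% is 6.4% (58/57) and 5.8% (40/75); at 11.2% it is 10.4% and 9.9%. Zelen's exact test is more conservative: 2.5% and 2.2% at 3.2%.

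**Power.** With a 3D SAE rate of 15% in one of two roughly equal strata and 3.2% elsewhere: Wald about 16%, likelihood ratio about 41% (partly from its inflated size), Firth about 35%.

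**Illustration.** One stratum 8/58 (3D) v 0/58 (control), the other 2/57 v 2/57. Interaction p-values: Wald about 1, likelihood ratio 0.019, Firth 0.045. Fisher's exact test within the first stratum gives p = 0.006, but a Wald gate would not lead there.

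**The case against.** **The 3.2% is a proxy.** It comes from an earlier study of the standard system, describes serious procedural complications among recanalized patients, and may be narrower than any device- or procedure-related SAE within 24 hours. The same study had 11.2% symptomatic ICH. This stands: at 6% the distortion is smaller, and by 9% it is minor with an even split.

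**The SAP does not name maximum likelihood or Wald.** Correct. It says only logistic regression, and a penalised fit would also qualify. The defect is that the choice is open, and the usual choices give very different answers.

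**The calculations use a full model, while SAP 9.4 lists no subgroup main effect.** Also correct. Taken literally with indicator coding, the tested term compares strata within the 3D arm. At 3.2% with an even split its size is 0.7% (Wald) or 19.3% (likelihood ratio), so the sparse-data problem remains.

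**Firth does not run at 10% either.** True at 3.2%, where it is conservative, but it is closer to nominal than the other tests for a two-level factor.

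**Harm would still show elsewhere.** A reader might infer that the gate could hide a safety signal altogether. The documents do not support that. In the illustration the overall comparison is 10/115 v 2/115, Fisher p = 0.034, below the 0.05 of SAP 10.1 (although not below 0.05/3 = 0.017 if the Bonferroni rule of SAP 10.4 is applied over three safety variables). SAEs are tabulated by subject, the CEC/DSMB monitors safety, and SAP 9.4 does not forbid looking within strata when the gate is not met.

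**Conclusion.** The point holds for the primary safety endpoint, and for safety variables by site of occlusion. If the SAE rate is near 3.2%, a two-level subgroup has an empty cell in about 49% to 60% of trials, and with an even split the 10% gate runs at about 1% (Wald) or 17% (likelihood ratio). By site an empty cell is nearly certain with three or four levels. At 6% and an even split the figures are 11% empty, Wald 5% and likelihood ratio about 13%; at 9%, about 2% empty.

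It would be tempting to say that all the safety subgroup tests fail for want of events. The documents do not support that: symptomatic ICH has about 13 expected events per arm and is near nominal by age or NIHSS unless the split is very uneven. Mortality has no stated rate; at an assumed 20–30% the two-level tests are close to 10%.

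Nor does the point touch the trial's conclusion, since SAP 2 keeps subgroups out of study success and product claims. It is a worthwhile, low-cost repair to a safety screen. The result rests on the assumed rate, splits and site levels, and on the full model.

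**What to change.** In SAP 9.4:

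- For the primary safety endpoint, and for any safety-by-factor table with an empty cell, test the interaction with a Firth penalised likelihood-ratio test. Name the test statistic for the remaining analyses.
- Always report events/patients and the risk difference by arm and stratum, whatever the interaction p-value.
- Analyse safety subgroups by treatment received, as SAP 5.1 and 10.1 do for safety, rather than ITT.
- Define collapsed site-of-occlusion groups before database lock.

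The cost is one procedure option, a set of count tables and a few sentences of SAP text. The drawback is that Firth is somewhat conservative at very low rates, about 6–7% for a nominal 10%, so the counts by stratum should carry most of the interpretation.
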